5.3 TREATMENT CYCLES

- One cycle of therapy is defined as 28 days (+/- 4 days). Patients will receive one cycle of therapy every 28 days (+/- 4 days).
- Cycles may be started early (but not earlier than day 24) for patients with active disease if judged in the best interest of the patient.
For the dose finding PF-04518600 monotherapy cohort, the DLT defining period is 28 days. As such, cycle 2 should not be commenced before 28 days for the patients being treated in the lead-in cohort.
- Subsequent cycles may be delayed for recovery of toxicity or other medical conditions (e.g. infections). Delays in the start of subsequent cycles greater than 8 weeks will be acceptable only for patients who are deriving clinical benefit and after discussion with the principal investigator of potential risk/benefit ratio and clear documentation in the medical record of the reason for continuation and perceived benefit to the patient from continuation of this therapy.
- In instances where one drug has to be discontinued transiently because of safety, the administration of the other drug/s may continue as scheduled.
- Therapy will be held during phase II of the study, for grade 4 neutropenia or grade 4 thrombocytopenia lasting \geq 42 days from the start of each cycle, in the absence of any evidence of active AML in the bone marrow or peripheral blood. Delays in start of subsequent cycles greater than 42 days will be acceptable only for patients who are deriving clinical benefit and after discussion with the principal investigator of potential risk/benefit ratio.
- If the peripheral counts do not recover (ANC $<0.5 \times 10^9/L$ and/or platelets $<25 \times 10^9/L$) but there is evidence of residual leukemia by morphology or flow-cytometry in the bone marrow, subsequent cycles can be administered at the discretion of the treating physician not earlier than 24 days after the prior cycle in

the phase II portion of the study.

- For patients who discontinue therapy, the reason for treatment discontinuation will be captured.

5.4 DOSE ADJUSTMENTS

5.4.1 Dose adjustments for hematological drug- related adverse events (AE):

- Dose reduction/interruption/discontinuation decisions should be based on the CTCAE version 4.03 (**Appendix**) and the guidelines provided below.

Patients with acute leukemias usually present with abnormal peripheral blood counts at the time therapy is started, and myelosuppression is an expected event during the course of therapy for acute leukemia. Thus, no dose adjustments or treatment interruptions for myelosuppression will be planned for the first 4 cycles in patients in whom myelosuppression is due to the presence of residual leukemia. After cycle 1, treatment interruptions and dose adjustments may be considered according to the following guidelines when there is no evidence of active leukemia (e.g., only if <5% blasts in the bone marrow or cytopenias not considered to be related to leukemia).

- Patients with a response (no evidence of any residual leukemia on bone marrow and/or peripheral blood) and pre-cycle counts of neutrophils $>1 \times 10^9/L$ and platelets $>50 \times 10^9/L$ will have dose modifications for hematological toxicities as specified in the azacitidine and gemtuzumab PIs and the venetoclax, avelumab, PF-04518600, and glasdegib IBs (**Appendix**)
 -
- If there are persistent peripheral blood blasts, or the bone marrow shows $>5\%$ blasts or any evidence of residual leukemia, treatment may be continued regardless of neutrophil and platelet count with supportive care as needed. Dose-interruptions of individual drugs in these patients should be considered on an individual case-by-case basis and discussed with the PI.
- Investigators should, whenever possible, determine which medication is causing the toxicity and interrupt or dose reduce, as applicable. No dose reductions (only dose interruptions as needed) are permitted for the IO-agents (avelumab and PF-04518600) in the phase II portion.
 - Patients who are experiencing ongoing dose delays >8 weeks due to unresolved grade ≥ 3 adverse events should be taken off treatment.

5.4.2 Dose adjustments for non-hematologic drug- related AEs

Investigators should, whenever possible, determine which medication is causing the toxicity and interrupt or dose reduce azacitidine, venetoclax, glasdegib, GO and/or interrupt IO-agents, as applicable (Table 3). No dose reductions (only interruptions) are permitted for the IO-agents (avelumab and **PF-04518600**) in the phase II portion.

Dose reductions of azacitidine will be as follows: dose level -1 of azacitidine: 50 mg/m² x 7 days, dose level -2: 37.5 mg/m² x 7 days, dose level -3: 25 mg/m² x 7 days. Further reductions beyond what is shown above or alternative reductions (e.g. 75mg/m² x 5 days) may be allowed if deemed in the patient's best interest by the treating physician.

Dose reductions of venetoclax will be as follows: dose level -1 of venetoclax: 200mg, dose level -2: 100mg, dose level -3, 50mg. Alternatively, the duration of venetoclax administration can be decreased (e.g. decrease from 21-day to 14-day administration) rather the dose being reduced.

The dose of GO is 3mg/m² and dose-reductions will not be done. In case of toxicity considered to be related to GO the dose/s of GO will be omitted.

Separate dose-modifications for glasdegib are presented in section 5.4.7 and should be followed for toxicities considered to be related to the glasdegib.

Table 3. Dose adjustments of azacitidine for non-hematologic drug-related AEs, clinically significant in the opinion of the investigator

Grade	Occurrence	Dose modification
1 or 2	Any time	No dose reduction
3 or 4 (Persistent grade 2: Consider similar dose adjustments if persistent and not responding to optimal management in the opinion of PI and treating physician)	1st and 2nd time	Hold suspected drug. Resume the held drug at prior dose if recovery to ≤ Grade 1 occurs within 14 days. If toxicity persists for 15-28 days, hold the drug and resume at prior dose if recovery to ≤ Grade 1 OR resume the drug at ONE dose level below current dose if recovery to ≤ Grade 2. Dose re-escalation to prior dose of the drug is permitted in accordance with the dose-escalation guidelines in section 5.4.7.
	3rd.	Hold suspected drug. Follow until toxicity ≤ Grade 2. Resume the held drug at ONE dose level below current dose. Dose re-escalation of the drug to prior dose is permitted in accordance with the dose-escalation guidelines outlined below Patients who are experiencing ongoing dose delays >8 weeks due to unresolved grade ≥3 adverse events should be taken off treatment.
	4th time	Discontinue therapy

5.4.3 IO-agent (avelumab and PF-04518600) dose delay/interruption for immune-oncology drug-related AEs, clinically significant in the opinion of the investigator

All IO-agent/s administration should be delayed for the following drug-related AEs, clinically significant in the opinion of the investigator:

- Any Grade ≥ 2 non-skin AE, except that
 - Grade 2 fatigue or laboratory abnormalities do not require delay, however patients with ALT or AST > 3 and up to 5 x ULN or total bilirubin greater > 2.0 mg/dL and up to 3 x ULN or creatinine > 2.0 mg/dL and up to 3 x ULN should have avelumab treatment withheld.

All IO agent/s administration should be delayed for the following drug-related AEs, clinically significant in the opinion of the investigator:

- Any Grade 3 skin AE, or Grade 3 laboratory abnormality, with the following exceptions:
 - Grade 3 lymphopenia or leukopenia does not require dose delay.
 - However, patients with drug-related ALT or AST > 5 x ULN or total bilirubin greater > 3 x ULN or creatinine > 3 x ULN should have avelumab treatment interrupted.
 - Any AE, laboratory abnormality, or intercurrent illness, which in the judgment of the investigator, warrants delaying the dose of study medication.
 - IO-agent dose reductions are not permitted in this study (only dose delays when indicated).

Subjects may resume treatment with study drug when the drug-related AE(s) resolve to Grade ≤ 1 or baseline value, with the following exceptions:

- Subjects may resume treatment in the presence of Grade 2 drug-related fatigue
- Subjects who have not experienced a Grade 3 drug-related skin AE may resume treatment in the presence of Grade 2 skin toxicity
- Drug-related pulmonary toxicity, diarrhea, or colitis, must have resolved to baseline or at least \leq grade 1 before treatment is resumed
- Drug-related endocrinopathies adequately controlled may resume treatment

If the criteria to resume treatment are met, the subject should restart treatment at the next scheduled time point per protocol. However, if the treatment is delayed past the next scheduled time point per protocol, the next scheduled time point will be delayed until dosing resumes. Patients who receive combination therapy in whom continuation of the non-IO agent(s) (e.g. azacitidine, GO and/or venetoclax) is considered to be inadequate, or inappropriate (e.g., because of pancytopenia or other considered related severe toxicity) can discontinue these agents and continue with IO-agent only.

Patients who are experiencing ongoing dose delays > 8 weeks due to unresolved grade ≥ 3 adverse events should be taken off treatment, except as specified in discontinuation section.

5.4.4 IO-agent Discontinuation Criteria: The following clinically significant, drug-related ADRs require permanent treatment discontinuation of any IO=agent/s:

---Any Grade 4 drug-related AEs require treatment discontinuation with IO-agent/s except for single laboratory values out of normal range that are unlikely related to study treatment as assessed by the Investigator, do not have any clinical correlate, and resolve within 7 days with adequate medical management

---Any Grade 3 drug-related AEs require treatment discontinuation with IO-agent/s except for any of the following:

- Transient (\leq 6 hours) Grade 3 flu-like symptoms or fever, which is controlled with medical management
- Transient (\leq 24 hours) Grade 3 fatigue, local reactions, headache, nausea, emesis that resolves to Grade \leq 1
- Single laboratory values out of normal range (excluding Grade \geq 3 liver function test increase) that are unlikely related to study treatment according to the Investigator, do not have any clinical correlate, and resolve to Grade \leq 1 within 7 days with adequate medical management
- Tumor flare phenomenon defined as local pain, irritation, or rash localized at sites of known or suspected tumor
- Change in ECOG PS to \geq 3 that does not resolve to \leq 2 within 14 days (infusions should not be given on the following cycle, if the ECOG PS is \geq 3 on the day of study drug administration)

Any Grade 2 drug-related AEs should be managed as follows:

- If a Grade 2 AE resolves to Grade \leq 1 by the last day of the current cycle, treatment may continue.
- If a Grade 2 AE does not resolve to Grade \leq 1 by the last day of the current cycle, infusions should not be given on the following cycle. If at the end of the following cycle the event has not resolved to Grade 1, the subject should permanently discontinue treatment with IO-agent/s (except for hormone insufficiencies, that can be managed by replacement therapy; for these hormone insufficiencies, up to 2 subsequent doses may be omitted).
- Upon the second occurrence of the same Grade 2 AE (except for hormone insufficiencies that can be managed by replacement therapy) in the same subject, treatment with the IO-agent/s has to be permanently discontinued unless the patient is deriving clinical benefit in which case the agent may be continued after discussion with the PI of potential risk/benefit ratio and documentation of this discussion in the patient's medical record.
- Infusion-related reactions, hypersensitivity reactions (Grades 1 to 4), and tumor lysis syndrome should be handled according to guidelines provided.
- Any dosing interruption due to drug-related toxicity lasting $>$ 8 weeks

5.4.5 Detailed management algorithms for immune-oncology drug-related adverse events (including gastrointestinal, renal, pulmonary, hepatic, endocrine, skin and neurological) are provided in Table 4 below. These general guidelines constitute guidance to the Investigator and may be supplemented by discussions with the PI and IND Office in specific cases.

Since IO-agent/s stimulates the immune system, immune-related AEs (irAEs) may occur. Treatment of irAEs is mainly dependent upon severity (NCI-CTCAE grade): Grade 1 to 2: treat symptomatically or with moderate dose steroids, more frequent

monitoring

Grade 1 to 2 (persistent): manage similar to high grade AE (Grade 3 to 4)

Grade 3 to 4: treat with high dose corticosteroids

Table 4. Management of Immune-Related Adverse Events (irAEs) (These are to be followed for toxicities with all immune agents included in this protocol including immune checkpoints and monoclonal antibodies)

Gastrointestinal irAEs		
Severity of Diarrhea / Colitis (NCI-CTCAE v4.03)	Management	Follow-up
Grade 1 Diarrhea: < 4 stools/day over Baseline Colitis: asymptomatic	Continue IO therapy/s Symptomatic treatment (for example, loperamide)	Close monitoring for worsening symptoms Educate subject to report worsening immediately If worsens: Treat as Grade 2 or 3/4
Grade 2 Diarrhea: 4 to 6 stools per day over Baseline; IV fluids indicated < 24 hours; not interfering with ADL Colitis: abdominal pain; blood in stool	Delay IO therapy/s Symptomatic treatment	If improves to Grade 1: Resume IO-therapy/s If persists > 5 to 7 days or recur: 0.5 to 1.0 mg/kg/day methylprednisolone or equivalent When symptoms improve to Grade 1, taper steroids over at least 1 month, consider prophylactic antibiotics for opportunistic infections, and resume IO-therapy/s per protocol. If worsens or persists > 3 to 5 days with oral steroids: Treat as Grade 3 to 4
Grade 3 to 4 Diarrhea (Grade 3): ≥ 7 stools per day over Baseline; incontinence; IV fluids ≥ 24 hrs; interfering with ADL Colitis (Grade 3): severe abdominal pain, medical intervention indicated, peritoneal signs Grade 4: life-threatening, perforation	Discontinue IO-therapy/s per protocol 1.0 to 2.0 mg/kg/day methylprednisolone IV or equivalent Add prophylactic antibiotics for opportunistic infections Consider lower endoscopy	If improves: Continue steroids until Grade 1, then taper over at least 1 month If persists > 3 to 5 days, or recurs after improvement: Add infliximab 5 mg/kg (if no contraindication), Note: Infliximab should not be used in cases of perforation or sepsis
Dermatological irAEs		

Grade of Rash (NCI-CTCAE v4.03)	Management	Follow-up
Grade 1 to 2 Covering \leq 30% body surface area	Symptomatic therapy (for example, antihistamines, topical steroids) Continue IO-therapy/s	If persists > 1 to 2 weeks or recurs: Consider skin biopsy Delay IO-therapy/s Consider 0.5 to 1.0 mg/kg/day methylprednisolone IV or oral equivalent. Once improving, taper steroids over at least 1 month, consider prophylactic antibiotics for opportunistic infections, and resume IO-therapy/s If worsens: Treat as Grade 3 to 4
Grade 3 to 4 Covering > 30% body surface area; life threatening consequences	Delay or discontinue IO-therapy/s Consider skin biopsy Dermatology consult 1.0 to 2.0 mg/kg/day methylprednisolone IV or IV equivalent	If improves to Grade 1: Taper steroids over at least 1 month and add prophylactic antibiotics for opportunistic infections Resume IO-therapy/s
Pulmonary irAEs		
Grade of Pneumonitis (NCI-CTCAE v4)	Management	Follow-up
Grade 1 Radiographic changes only	Consider delay of IO-therapy/s Monitor for symptoms every 2 to 3 days Consider Pulmonary and Infectious Disease consults	Re-image at least every 3 weeks If worsens: Treat as Grade 2 or Grade 3 to 4
Grade 2 Mild to moderate new symptoms	Delay IO-therapy/s Pulmonary and Infectious Disease consults Monitor symptoms daily, consider hospitalization 1.0 mg/kg/day methylprednisolone IV or oral equivalent Consider bronchoscopy, lung biopsy	Re-image every 1 to 3 days If improves: When symptoms return to near Baseline, taper steroids over at least 1 month and then resume IO-therapy/s and consider prophylactic antibiotics If not improving after 2 weeks or worsening: Treat as Grade 3 to 4
Grade 3 to 4	Discontinue IO-	If improves to Baseline:

Severe new symptoms; New / worsening hypoxia; life-threatening	therapy/s Hospitalize Pulmonary and Infectious Disease consults 2 to 4 mg/kg/day methylprednisolone IV or IV equivalent Add prophylactic antibiotics for opportunistic infections Consider bronchoscopy, lung biopsy	Taper steroids over at least 6 weeks If not improving after 48 hours or worsening: Add additional immunosuppression (for example, infliximab, cyclophosphamide, IV immunoglobulin, or mycophenolate mofetil)
Hepatic irAEs		
Grade of Liver Test Elevation (NCI-CTCAE v4)	Management	Follow-up
Grade 1 Grade 1 AST or ALT > ULN to 3.0 x ULN and / or total bilirubin > ULN to 1.5 x ULN	Continue IO-therapy/s	Continue liver function monitoring If worsens: Treat as Grade 2 or 3 to 4
Grade 2 AST or ALT > 3.0 to \leq 5 x ULN and / or total bilirubin > 1.5 to \leq 3 x ULN	Delay IO-therapy/s Increase frequency of monitoring to every 3 days	If returns to Baseline: Resume routine monitoring, resume IO-therapy/s If elevations persist > 5 to 7 days or worsen: 0.5 to 1 mg/kg/day methylprednisolone or oral equivalent and when LFT returns to Grade 1 or Baseline, taper steroids over at least 1 month, consider prophylactic antibiotics for opportunistic infections, and resume IO-therapy/s
Grade 3 to 4 AST or ALT > 5 x ULN and / or total bilirubin > 3 x ULN	Discontinue IO-therapy/s Increase frequency of monitoring to every 1 to 2 days 1.0 to 2.0 mg/kg/day methylprednisolone IV or IV equivalent Add prophylactic antibiotics for opportunistic infections Consult	If returns to Grade 2: Taper steroids over at least 1 month If does not improve in > 3 to 5 days, worsens or rebounds: Add mycophenolate mofetil 1 gram (g) twice daily If no response within an additional 3 to 5 days, consider other immunosuppressants per local guidelines

	gastroenterologist Consider obtaining MRI/CT scan of liver and liver biopsy if clinically warranted	
Endocrine irAEs		
Endocrine Disorder	Management	Follow-up
Asymptomatic TSH abnormality	Continue IO-therapy/s If TSH < 0.5 x LLN, or TSH > 2 x ULN, or consistently out of range in 2 subsequent measurements: include T4 at subsequent cycles as clinically indicated; consider endocrinology consult	
Symptomatic endocrinopathies	Evaluate endocrine function Consider pituitary scan Symptomatic with abnormal lab / pituitary scan: Delay IO-therapy/s 1 to 2 mg/kg/day methylprednisolone IV or by mouth equivalent Initiate appropriate hormone therapy No abnormal lab / pituitary MRI scan but symptoms persist: Repeat labs in 1 to 3 weeks / MRI in 1 month	If improves (with or without hormone replacement): Taper steroids over at least 1 month and consider prophylactic antibiotics for opportunistic infections Resume IO-therapy/s Subjects with adrenal insufficiency may need to continue steroids with mineralocorticoid component
Suspicion of adrenal crisis (for example, severe dehydration, hypotension, shock out of proportion to current illness)	Delay or discontinue IO-therapy/s Rule out sepsis Stress dose of IV steroids with mineralocorticoid activity IV fluids Consult endocrinologist If adrenal crisis ruled out, then treat as above for symptomatic endocrinopathies	
Cardiac irAEs		
Myocarditis	Management	Follow-up
New onset of cardiac signs or symptoms and / or new laboratory cardiac biomarker elevations (e.g. troponin, CK-MB, BNP) or cardiac imaging abnormalities suggestive of myocarditis.	Withhold IO therapy Hospitalize. In the presence of life threatening cardiac decompensation, consider transfer to a facility experienced in advanced heart failure and arrhythmia	If symptoms improve and immune-mediated etiology is ruled out, re-start IO therapy. If symptoms do not improve/worsen, viral

	
management.
 
Cardiology consult to establish etiology and rule-out immune-mediated myocarditis.
 
Guideline based supportive treatment as appropriate per cardiology consult.*
 
Consider myocardial biopsy if recommended per cardiology consult.
	
myocarditis is excluded, and immune-mediated etiology is suspected or confirmed following cardiology consult, manage as immune-mediated myocarditis.

Immune-mediated myocarditis	
Permanently discontinue avelumab.
 
Guideline based supportive treatment as appropriate per cardiology consult.*
 
Methylprednisolone 1-2 mg/kg/day.
	
Once improving, taper steroids over at least 1 month and add prophylactic antibiotics for opportunistic infections.
 
If no improvement or worsening, consider additional immunosuppressions (e.g. azathioprine, cyclosporine A)

*Local guidelines, or eg. ESC or AHA guidelines

ESC guidelines website:

<https://www.escardio.org/Guidelines/Clinical-Practice-Guidelines>

AHA guidelines website:

<http://professional.heart.org/professional/GuidelinesStatements/searchresults.jsp?q=&y=&t=1001>

ADL = activities of daily living; ALT = alanine aminotransferase; AST = aspartate aminotransferase; CT = computed tomography; irAE = immune-related adverse event; IV=intravenous; LFT = liver function test; LLN = lower limit of normal; MRI = magnetic resonance imaging; NCI-CTCAE = National Cancer Institute-Common Terminology Criteria for Adverse Event; T4 = free thyroxine; TSH = thyroid-stimulating hormone; ULN = upper limit of normal.

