3.4 DLT Definition

DLT is defined as clinically significant non-hematologic adverse event or abnormal laboratory value assessed as unrelated to disease progression, intercurrent illness, or concomitant medications and occurring during the first cycle (28 days) on study that meets any of the following criteria:

- CTCAE Grade 3 AST (SGOT) or ALT (SGPT) for $>/= 7$ days or grade 3 hyperbilirubinemia for $>/= 7$ days

- CTCAE Grade 3 AST (SGOT) or ALT (SGPT) accompanied by grade 2 bilirubin increase
- CTCAE Grade 4 AST (SGOT) or ALT (SGPT) of any duration
- All other clinically significant non-hematological adverse event that is Grade 3 or 4 according to the NCI common terminology criteria version 4.0 with the following exceptions:
 - Grade 3 or 4 nausea, vomiting and diarrhea will be considered DLT only if not controlled by optimal therapy within 72 hours.
 - Grade 3 biochemical abnormalities (e.g., lipase or bilirubin elevation) will only be considered DLT if accompanied by clinical consequences. Grade 3 or 4 electrolyte abnormalities will only be considered DLT if possibly related to study drug and not corrected by optimal replacement therapy within 72 hours.
- Results in discontinuation of therapy
- Any treatment-related death;

Grade 4 neutopenia lasting \geq 42 days from start of cycle in absence of evidence of active AML.

For patients in venetoclax-containing arms (i.e. Arms B and D) who do not receive venetoclax on day 1 due to logistical and/or financial reasons, the DLT period will be extended to 28 days from the first dose of venetoclax. For evaluation of neutropenia-related DLT, the DLT period will be 42 days from the first dose of venetoclax. Evaluation of the first 6 patients in each of the venetoclax containing treatment arms (arms B and D) will occur after all patients have completed two cycles of treatment (or at least 56 days from the first dose of venetoclax). Enrollment will be halted while the first 6 patients in each of these treatment arms are evaluated for safety.

Please see statistics section (section 11.0) for efficacy and toxicity stopping rules to be applied independently to each cohort.

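### For the same drug-related Grade 3 skin or laboratory event, section 5.4.3 pauses and resumes the IO agent while section 5.4.4 stops it permanently; the DLT count is at risk only for a narrow set of laboratory events

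*Combined protocol and SAP*

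**What the plan says.** **Section 5.4.3 (delay or interruption).** Among the drug-related, clinically significant reasons to delay all IO agents is "Any Grade 3 skin AE, or Grade 3 laboratory abnormality, with the following exceptions". On return it says "Subjects may resume treatment with study drug when the drug-related AE(s) resolve to Grade ≤ 1 or baseline value". For higher liver or kidney values, patients with drug-related ALT or AST above 5 x ULN or "total bilirubin greater > 3 x ULN or creatinine > 3 x ULN should have avelumab treatment interrupted".

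**Section 5.4.4 (permanent discontinuation).** For clinically significant, drug-related reactions: "Any Grade 3 drug-related AEs require treatment discontinuation with IO-agent/s except for any of the following". The listed exceptions include brief flu-like symptoms, brief fatigue or local reactions, tumor flare (which can include a localized rash), and single laboratory values judged unlikely to be related to treatment. That last item leaves out liver test rises of Grade 3 or more. The list also contains an item on ECOG status of 3 or worse that does not recover.

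**Table 4 (section 5.4.5).** The Grade 3 to 4 rash row reads "Delay or discontinue IO-therapy/s Consider skin biopsy", and its follow-up column resumes the IO agent after improvement to Grade 1. The Grade 3 to 4 liver row reads "Discontinue IO-therapy/s Increase frequency of monitoring to every 1 to 2 days" and mentions no resumption.

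**Section 3.4 (DLT definition).** One criterion is "Results in discontinuation of therapy", with no statement of which agent or agents it refers to. One exception is "Grade 3 biochemical abnormalities (e.g., lipase or bilirubin elevation) will only be considered DLT if accompanied by clinical consequences". Grade 3 AST/ALT or bilirubin counts when it lasts 7 days or more, and Grade 3 AST/ALT also counts when accompanied by a Grade 2 bilirubin increase.

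**Section 3.3 and section 11.0 (lead-in).** At most 1 DLT in 6 lets the arm continue; 2 or more sends the next 6 patients to a lower dose level.

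**The concern.** A treating physician who opens section 5.4.3 would hold avelumab and restart it. One who opens section 5.4.4 for the same event would never restart it. Both sections carry the same two qualifiers (drug-related, and clinically significant in the investigator's opinion), so they describe the same patients. The direct stake is patient safety and consistent treatment in Arms C and D.

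There is a possible second stake. Because discontinuation is itself a DLT criterion, an event that section 3.4 would otherwise leave out might be counted or not, depending on which IO section was followed. In a six-patient lead-in, a single patient separates continuing from going to a lower dose level.

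**Working it through.** **1. The clinical texts side by side (clinically significant, drug-related, Grade 3)**

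| Event | 5.4.3 | 5.4.4 | Table 4 |
|---|---|---|---|
| Ordinary drug rash | delay, may resume | permanent stop | delay or discontinue, then resume |
| ALT/AST > 5 x ULN or bilirubin > 3 x ULN | interrupt avelumab | permanent stop | discontinue |
| Other laboratory abnormality, not covered by the lymphopenia/leukopenia exception in 5.4.3 | delay, may resume | permanent stop | not needed for the conflict |

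The two sections cannot be read as successive steps. Section 5.4.4 is triggered by grade, not by persistence or recurrence. Section 5.4.3 takes rechallenge after a Grade 3 skin event for granted: such a history only removes the allowance to restart while Grade 2 skin toxicity remains. The one cross-reference from 5.4.3 to the discontinuation section concerns delays beyond 8 weeks. No precedence clause was found.

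**2. Which events could change the DLT count**

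- *Skin.* Under section 3.4 a clinically significant Grade 3 non-hematologic event in the DLT window is already a DLT, subject to the general attribution wording, whether or not the agent is stopped. The count is the same under either IO section.
- *Laboratory.* A Grade 3 biochemical abnormality without clinical consequences, or Grade 3 AST/ALT or bilirubin lasting under 7 days, can fall outside the DLT definition. If the investigator still judges it clinically significant, 5.4.4 mandates a stop. That stop may then meet the discontinuation criterion, whereas a delay under 5.4.3 would not. This requires that stopping one agent of a triplet counts as discontinuing therapy, which is undefined.

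**3. The plan's own toxicity figures for Arms C-D**

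Inputs from section 11.0: prior Beta(0.3, 1.7); stop if Pr(P_T > 0.15 | data) > 0.80; looks at 6, 9, 12 and 15; maximum 18. With y DLTs in n patients the posterior is Beta(0.3 + y, 1.7 + n − y).

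- Upper tail at 0.15: 2/6 gives 0.801, 3/9 gives 0.873, 4/12 gives 0.916, 4/15 gives 0.839. These boundaries match Table 20. One DLT in 6 gives 0.450.
- Exact early-stop probabilities at true rates 0.10, 0.15, 0.20, 0.25, 0.30 and 0.40 are 0.143, 0.302, 0.481, 0.647, 0.781 and 0.937. Table 21 states 0.137, 0.290, 0.485, 0.653, 0.771 and 0.936. The largest gap is about 0.012, so the plan's figures are reproduced.

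**4. Effect of reclassification on the lead-in**

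P(X ≥ 2) = 1 − (1 − p)^6 − 6p(1 − p)^5, with X ~ Bin(6, p).

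- p = 0.15: 1 − 0.3771 − 0.3993 = 0.224
- p = 0.17: 1 − 0.3269 − 0.4018 = 0.271
- p = 0.20: 1 − 0.2621 − 0.3932 = 0.345

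The documents give no rate for these laboratory events. The base rate and the added share q (patients whose event is a DLT only through the mandated stop) are therefore assumptions:

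| Base DLT rate | q = 0 | q = 0.02 | q = 0.05 |
|---|---|---|---|
| 0.10 | 0.114 | 0.156 | 0.224 |
| 0.15 | 0.224 | 0.271 | 0.345 |
| 0.20 | 0.345 | 0.394 | 0.466 |

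**The case against.** The case for leaving the text alone has several parts.

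- *Table 4 is labelled as guidance and partly agrees with 5.4.4.* This is true of the liver row, and a reader who infers that Table 4 generally supports pausing would be wrong: even the rash row offers either action. But 5.4.3 is not labelled as guidance, and it conflicts with 5.4.4 directly.
- *Section 5.4.4 does have some skin exceptions.* Tumor-flare rash and transient local reactions are covered. Ordinary drug rash is not.
- *The DLT link is conditional.* This stands. An asymptomatic value judged not clinically significant never enters 5.4.4. Section 5.3 lets other drugs continue when one is stopped temporarily, and 5.4.3 lets patients drop the non-IO drugs and stay on treatment, so therapy could mean the whole regimen. What remains is an undefined term.
- *The size is assumed.* This also stands. A reader might take a 10-point rise, from 15% to 25%, which gives 0.466; nothing in the documents supports a shift that large. Section 2.6.2 reports no DLTs in the 12 phase Ib patients on azacitidine plus avelumab, although Arms C and D each add a third drug.
- *Central review.* Section 3.3 requires Medical Monitor approval before accrual passes six patients. That may catch a disputed DLT call, but it does not tell the treating physician which IO section to follow.

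Two further inferences are tempting and not supported. The bilirubin wording in the DLT exception need not contradict the 7-day bullet: the exception sits under events other than those already listed, so it can be read as covering shorter elevations. The ECOG item in the 5.4.4 list is not plain permission to dose, because it also withholds infusions when ECOG is 3 or worse on the dosing day; its role in the list is unclear.

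**Conclusion.** The contradiction between 5.4.3 and 5.4.4 is established by the text and needs no assumption. Table 4's rash row is in tension with 5.4.4, and its liver row conflicts with 5.4.3. The affected open arms are C and D. Arm B contains neither of the agents that 5.4.3 names as IO agents, and Arms A and E are closed. This alone justifies reconciling the passages, since the outcomes are rechallenge and permanent stop.

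It would be wrong to infer that the conflict alters the DLT count for skin events. A change is possible only for otherwise exempt laboratory events in the DLT window that are judged clinically significant, and only if a mandated stop of one IO agent meets the discontinuation criterion. Where both hold, one patient can move an arm from 1/6 to 2/6. At an assumed 15% base rate, an assumed 2 to 5 percentage points moves the chance of a lower dose level from 0.22 to 0.27–0.34. This illustrates sensitivity and is not an estimate of what will happen.

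**What to change.** 1. Reconcile sections 5.4.3 and 5.4.4 and the matching Table 4 rows so that each drug-related Grade 3 event has one stated action, or add a sentence saying which section prevails.
2. Clarify whether the ECOG item in the 5.4.4 list is meant as an exception to stopping or as a criterion for it.
3. In section 3.4, state whether discontinuation of therapy includes protocol-mandated stopping of a single IO agent for an event that the laboratory exception would otherwise leave out.

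Which clinical action applies is for the sponsor to decide; this review proposes none. The cost is amendment wording, with no new procedures and no additional patients.
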